Due to the problem of attrition in the control group, it has been suggested in the last International Myopia Conference that controlled field studies be performed by a virtual group, without performing a non-inferiority study, since atropine 0.01% could not be taken as gold standard because it is not yet approved and as we said, it is off-label in Argentina. Data on progression in Asia or Europe could be used for this virtual control group, but it would be more convenient to have a virtual control group in one's own living environment. In the case of our country there is already a possible control group of 114 children of 12 years of age on average who were followed up with cycloplegia during the years pre-pandemic and from which it is known that the progression was from 0.43+/-0.52 diopters in one year.³⁶

It is thus proposed to perform a prospective clinical study in 100 children who will be enrolled when in the usual consultation for their eyeglasses control they can choose to do the treatment accessible in our environment (the diluted atropine drop) or a treatment that is possibly equally effective with special glasses designed in our environment. It is

expected that there will be similarity of effect on progression because the lens is based on the principles of defocusing of eyeglasses and contact lenses already proven by the international industry.³⁷ Our lens has the characteristic of being much simpler in its carving and construction, making it more economical for our environment where it has already been presented from the theoretical point of view.³⁸

Moreover, the special myopia control spectacle lacks the possible toxic effects of a drop instilled in the eye for many years until emerging adulthood. In addition, to avoid including children who may have rapid progressions to high myopia, treatment will be offered only to children over 8 years of age. In our environment, where children are outdoors a lot, the progression is slower than in Asian countries and is around -0.50 diopters per year, as we said.³⁶ A strong myopia is the one that exceeds -5.00 diopters.³⁹ Thus the risk for a child included in this project is to progress -0.25 diopters in six months (the resolution limit of the measurement method), so each child who does not respond well with arrest of progression at six months may be removed from the protocol and switched to atropine treatment.

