Given the above-mentioned background, the following study has been designed to evaluate the arrest of myopia progression with the daily use of nationally designed glasses, comparing such progression with a virtual control group of similar age in a population of myopic children and adolescents of the same environment in our country.

WORKING HYPOTHESIS

The nationally designed lenses can be as effective as the proven international industry designs that have been subjected to controlled trials against natural history of the disease.

PURPOSE

To treat a group of consecutive volunteer patients who choose between the affordable treatment in our environment (daily diluted atropine drops for several years) or the special lenses for myopia control designed by the National Industry. The purpose is to compare the progression during one year with the national lenses with respect to the progression with the foreign lenses and/or with the natural history of a virtual control group.

OBJECTIVES

Primary

To assess whether the intervention with locally designed spectacles is well tolerated and adhered to with daily use in childhood and adolescence.

Secondarily

To assess whether intervention with locally designed glasses can control myopia progression in childhood and adolescence.

DEFOCUS GLASSES OF NATIONAL DESIGN

The design of the national defocus lens is based on the original design presented by Carly Lam,⁴⁰ with a 9 mm central zone for distance correction and a correction ring with a +3.50 dioptre defocus between 9 and 32 mm in diameter to act in principle on the para foveal zone which is the one that detects the defocus that governs the growth of the eye.⁴¹ Instead of peripheral defocusing micro lenses that do not alter the visual field in the area of the 32

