ophthalmology offices that are members of the research team. The opticians and ophthalmologists will be asked to watch a video on myopia control developed by the principal investigators where this treatment methodology is explained during the evaluation process at the center of care. The opticians will verify the optical centration in the frames chosen ad hoc, with a modern digital centration system provided by the sponsors. After 15 days, when the glasses with the correct centering are ready, the subjects will go to the optician's office to try on the glasses in that room. On this occasion, as always in these cases, the optician will evaluate the subject's adaptation and mobility in the optician's shop, instructing the child to wear the glasses at home for a couple of days and then to wear them for as long as possible.

SAMPLE AND SAMPLE SIZE

The sample size will be 50 subjects of both genders to compare with the studies abroad that consist of an n between 40 and 90 subjects and the natural history in our country that counted 114 subjects. There will be a group of subjects who will be treated with the nationally designed defocus glasses. Statistical calculation for a difference of 0.25 diopters in progression with respect to controls, for a standard deviation of 0.50 diopters gives an $n = 31$ subjects and taking into account a 20% loss to follow-up the n should equal 38 subjects in the group. Thus reaching 50 subjects exceeds expectations.

METHODS

This field study to test tolerance and percentage of effectiveness of defocus lenses in the control of myopia will include boys and girls from 8 to 15 years of age who voluntarily

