One month after the delivery of the spectacle, the principal investigator in charge will make a telephone call to the parent of the study subject conducting the tolerance survey and thus verifying adherence to spectacle use. The survey is detailed in the attached medical record and responses will be uploaded into the computerised web-based system that will be developed for this study. The system will automate the alerts for these safety calls with automatic emails sent to the principal investigator in the month of spectacle delivery.

PLAN FOR ANALYSING THE RESULTS

The results of numerical variables shall be expressed as mean and standard deviation or median and interquartile range according to whether they are normally or skewed. Nominal variables will be expressed as absolute frequency and percentage. For the comparison of numerical variables, Student's t-test or Mann Whitney U-test will be used as appropriate. Nominal variables will be compared using the Chi-square test or Fisher's exact test as appropriate. A p-value of $p \leq 0,05$.

HUMAN RESOURCES

[name] and [name] are in charge of the design and control of the research. Statistical analysis will be performed by [name]. Physicians accredited to treat patients will have to demonstrate the ability to perform routine consultations for myopia control, refraction studies under cycloplegia and optical biometry. Once accredited, they will have a username and password to upload their data into the web form. Accredited doctors will be in permanent communication with doctors [name] and [name]. There will be a myopia progression monitoring system within the computerised system that will send reports if any child progresses more than 0.25 dioptres in six months to alert researchers so that precautionary measures can be taken in such cases.

MATERIAL RESOURCES

Optotypes, Retinoscope, Autorefractometer and Biometer posters of accredited institutions.

Approximately four institutions with a high turnover of paediatric consultations are expected to be accredited for an estimated enrolment time of 6 months.

Peripheral defocus spectacles will be provided by the sponsor (NOVAR) free of charge to all study subjects for one calendar year with the possibility of extending the study for two years. At the end of the study, if the expected positive results are found, the glasses will remain in the possession of the study subjects.

FINANCIAL RESOURCES

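### The equal-effectiveness hypothesis and the foreign-lens comparator have no matching analysis, while the rest of the plan supports superiority over the natural-history group

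*Combined protocol and SAP*

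**What the plan says.** The Working Hypothesis section has one sentence: "The nationally designed lenses can be as effective as the proven international industry designs that have been subjected to controlled trials". The Purpose section compares one-year progression with the national lenses "with respect to the progression with the foreign lenses and/or with the natural history of a virtual control group". Sample and Sample Size repeats the foreign comparison, setting 50 subjects "to compare with the studies abroad that consist of an n between 40 and 90 subjects" alongside the 114 natural-history children.

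Other parts name a single, local comparator. The design statement just before the Working Hypothesis speaks of "comparing such progression with a virtual control group of similar age". The secondary objective is "To assess whether intervention with locally designed glasses can control myopia progression in childhood and adolescence", with no mention of foreign lenses. The sample-size calculation is for a 0.25 D difference from controls. Methods identifies the virtual control group as the 114 children followed in 2018-2019.

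For the analysis, Plan for Analysing the Results says: "For the comparison of numerical variables, Student's t-test or Mann Whitney U-test will be used as appropriate". Chi-square or Fisher tests cover nominal variables, and the threshold is p ≤ 0.05. The plan gives no equivalence or non-inferiority margin and no confidence-interval rule. It designates no foreign dataset as comparator and has no rule for choosing between the two comparators.

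**The concern.** A difference test can reject equality; failing to reject does not demonstrate it. With a hypothesis of similarity, a difference test and no rule for interpretation, a non-significant comparison with a foreign study could be read as confirming the hypothesis. That outcome becomes more likely as the sample shrinks or dropout rises. The open comparator adds to this, because the plan does not say which comparison carries the efficacy conclusion.

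What is at stake is the efficacy statement in the final report: a claim that a simpler, cheaper lens performs as well as established designs, resting on a test that cannot support it.

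**Working it through.** **1. What the plan's own sample size answers.** Inputs from Sample and Sample Size: difference 0.25 D, SD 0.50 D, stated n = 31. Power and sidedness are not stated; I assume 80% and two-sided 0.05. The one-sample normal formula gives n = (0.50 × (1.960 + 0.842) / 0.25)² = 31.4, which matches 31. This is a calculation for detecting a difference from controls. Nothing in the section is sized for similarity.

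**2. Whether the planned tests suit the natural-history question.** With 20% loss, 50 × 0.8 = 40 evaluable. Against 114 controls, SE = 0.50 × √(1/40 + 1/114) = 0.0919 D. Power for 0.25 D is Φ(0.25/0.0919 − 1.96) = Φ(0.76), about 78%. The tests fit this question, with reasonable power.

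**3. What a comparison with a foreign study could show.** Inputs and assumptions:
- SD 0.50 D in both groups (Sample and Sample Size); 40 evaluable children.
- Foreign group of m = 40 or 90 (same section).
- Full lens effect = 60% (Problem Statement) × 0.43 D (Current State of Research) = 0.258 D. This applies the local untreated rate to the foreign studies, because the documents give no foreign rate in dioptres.
- Two-sided t-test at 0.05.

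SE = 0.50 × √(1/40 + 1/m); half-width = 1.96 × SE. Power is from the noncentral t with 40 + m − 2 degrees of freedom and noncentrality δ/SE. A lens keeping half the effect falls short by δ = 0.258/2 = 0.129 D; a lens with no effect by δ = 0.258 D.

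| Foreign n | SE (D) | 95% CI half-width (D) | p > 0.05, half effect kept | p > 0.05, no effect |
|---|---|---|---|---|
| 40 | 0.1118 | 0.219 | 79.3% | 37.5% |
| 90 | 0.0950 | 0.186 | 72.9% | 23.1% |

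The half-width of 0.19 to 0.22 D is most of the assumed full effect. With all 50 children evaluable, the non-significance rates are 69% to 77% (half effect) and 17% to 33% (no effect).

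**4. Sensitivity to the assumed effect.** The Problem Statement also cites a 40% reduction for a multifocal contact lens: 0.40 × 0.43 = 0.172 D. With 40 evaluable, half the effect kept (δ = 0.086 D) gives p > 0.05 in 85% to 88% of trials, and no effect (δ = 0.172 D) in 56% to 67%. A higher untreated rate abroad would enlarge the effect in dioptres and lower these rates.

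**5. What a real similarity claim would need.** No margin is given. If the margin were half of 0.258 D, then with concurrent 1:1 arms, one-sided 0.025, 80% power and no true difference, n per arm = 2 × (1.960 + 0.842)² × 0.50² / 0.129² = 236. A margin of 0.25 D needs 63 per arm but concedes the whole planned effect.

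**The case against.** The strongest reply is that the operative design is already the natural-history comparison. The design statement, secondary objective, sample-size calculation and Methods all point there, and the difference tests suit it. This stands. It confines the problem to the hypothesis sentence, the foreign-lens part of the Purpose and one clause on sample size. It does not remove the problem, because those passages still set a similarity question that nothing in the plan answers.

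Four stronger readings are tempting and are not supported:

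- A reader might infer that the plan rules out non-inferiority against foreign lenses, from the phrase "without performing a non-inferiority study" in Current State of Research. That passage reports a conference suggestion, and its reason is that atropine 0.01% is unapproved and cannot serve as the standard. It says nothing about foreign lenses and is no evidence for this point.
- A reader might infer that the plan will treat p > 0.05 as equality. No section says so, and the analysis plan is generic: it does not assign a t-test to the foreign comparison. The misreading is left open, not prescribed.
- A reader might infer that any clearly worse lens would usually pass as equal. In the 60% illustration this holds for partial loss of effect only. A lens with no effect would be detected 62% to 77% of the time.
- A reader might infer that the wording was left open so the comparator could be picked after the results. It equally permits reporting both comparisons, and the local control is already identified. The fair criticism is that no priority is stated.

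**Conclusion.** The point holds in a limited form. The similarity hypothesis and the foreign-lens comparator have no corresponding analysis, and they conflict with the parts of the protocol that define a superiority question against the 114 children. Non-significance against a foreign study would not support equal effectiveness. Under the stated assumptions it would occur 73% to 79% of the time with half the effect lost, and about 23% to 38% of the time with all of it lost.

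These percentages are illustrative. They depend on SD 0.50 D, 40 evaluable children, and a 60% effect carried over to the local 0.43 D rate. The logical gap does not depend on them. It concerns the secondary efficacy objective only; tolerance and adherence, the primary objective, are untouched. It should be corrected, but it does not invalidate the trial.

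**What to change.** - **Hypothesis and Purpose:** restate both as slower one-year progression with the national lens than in the 114-child natural-history group, and remove foreign lenses as a tested comparator. Amend the matching clause in Sample and Sample Size.
- **Analysis plan:** name this as the efficacy comparison. Report the difference in mean progression and the percentage reduction, each with a 95% confidence interval that reflects uncertainty in the control mean as well. Settle one control value first, since the documents give both 0.43 D and 0.45 D.
- **Foreign results:** show them descriptively beside that interval, and state that p > 0.05 against a foreign study is not evidence of equal effectiveness.

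The cost is protocol wording and the interval estimates, with no extra children or visits. The downside is a less ambitious efficacy claim. If the sponsor prefers to keep the similarity claim, the plan must name the foreign dataset, justify a margin in advance and judge by the confidence interval. The planned 50 children would be far too few for a half-effect margin, and differences between populations would still confound an indirect comparison.

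### The working hypothesis is parity with foreign lenses, but the plan contains only difference tests, with no margin or interval rule, so it has no valid way to support that claim

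*Combined protocol and SAP*

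**What the plan says.** The Working Hypothesis section contains the protocol's only stated hypothesis: "The nationally designed lenses can be as effective as the proven international industry designs". The Purpose section plans to set one-year progression on the national lens against progression "with respect to the progression with the foreign lenses and/or with the natural history of a virtual control group". Sample and Sample Size fixes 50 subjects, partly to "compare with the studies abroad that consist of an n between 40 and 90 subjects".

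The same section's calculation addresses another question: a difference of 0.25 D from controls with SD 0.50 D, giving n = 31, or 38 after allowing for 20% loss. On analysis, the Plan for Analysing the Results says: "For the comparison of numerical variables, Student's t-test or Mann Whitney U-test will be used as appropriate". It adds chi-square or Fisher's exact test for nominal variables and a 0.05 threshold. No section gives an equivalence or non-inferiority margin, or a confidence-interval rule.

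Current State of Research reports a suggestion to use a virtual control group "without performing a non-inferiority study, since atropine 0.01% could not be taken as gold standard". The reason given there concerns atropine, not the foreign lenses. The primary objective is tolerance and adherence; control of progression is secondary.

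**The concern.** Student's t and Mann-Whitney tests take no difference as the null. They can give evidence against parity but not for it. A significantly worse result contradicts the hypothesis, and a non-significant one may reflect either similar lenses or too little information. Without a margin or an interval rule, nothing in the plan separates those two cases.

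If a report then treated a non-significant difference from the foreign studies as confirming the hypothesis, dropout and noise would make the claim easier to reach. A lens with clearly less effect than the proven designs could be described as their equal. This matters because Current State of Research offers the lens to families as a possible alternative to atropine drops.

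**Working it through.** **The plan's own figure.** Treating the control mean as a fixed value, at two-sided 0.05 and 80% power (power is not stated, so this is assumed):

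n = [0.50 × (1.96 + 0.84) / 0.25]² ≈ 31.4, in line with the stated 31. Then 31 × 1.2 = 37.2, rounded up to 38.

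The figure reproduces as a test for a difference from controls. It does not size a parity claim.

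**Inputs for the foreign comparison.**
- Completers: 50 × (1 − 0.20) = 40 (Sample and Sample Size).
- Foreign n: 40 to 90 (same section).
- Local untreated progression: 0.43 ± 0.52 D/year in 114 children (Current State of Research).
- Foreign effect: 60% reduction (Problem Statement).
- Assumptions: the 60% carries over to the local rate, SD is 0.52 in every group (the documents give no foreign SD), changes are normal, and the test is two-sided at 0.05.

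**True differences from the foreign lens.**
- No-effect lens: 0.60 × 0.43 = 0.258 D.
- Half-effect lens: 0.258 / 2 = 0.129 D.

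**Standard error and 95% CI half-width.** SE = 0.52 × √(1/40 + 1/n₂).
- n₂ = 40: SE = 0.116, half-width = 1.991 × 0.116 = 0.231 D.
- n₂ = 90: SE = 0.099, half-width = 1.979 × 0.099 = 0.196 D.

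**Probability of p > 0.05 against the foreign lens** (noncentral t, two-sample t-test):

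| True national lens | Completers | n₂ = 40 | n₂ = 90 |
|---|---|---|---|
| Half effect (0.129 D worse) | 40 | 80.5% | 74.6% |
| No effect (0.258 D worse) | 40 | 40.8% | 26.4% |
| No effect (0.258 D worse) | 50 | 36.2% | 20.2% |

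**Adding the comparison with the 114 controls.** Simulating all three groups under the same assumptions, with 40 completers, gives the proportion of trials that are both non-significant against the foreign lens and significantly better than the controls:
- half-effect lens: about 26%;
- no-effect lens: about 2%.

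**Could a margin be met?** Take a margin of 0.129 D/year, half of the 60% effect, for illustration only. If the two lenses were truly equal, the 95% CI would exclude a loss of that size in 19.4% (n₂ = 40) to 25.3% (n₂ = 90) of trials. The half-width of 0.196 to 0.231 D is larger than this margin and close to the whole 0.258 D effect.

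**The case against.** The strongest reply is that the harmful decision rule is not in the document. The analysis paragraph is generic. It does not say its tests will be applied to foreign-lens data, or that p > 0.05 will be taken as parity. A descriptive comparison with published foreign results fits the text equally well. That stands: a reader might infer that support for the hypothesis can come only from non-significance, but the documents do not say so. What remains is that the plan gives no valid route to its stated hypothesis and no warning against the invalid one.

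Second, the operative design is against natural history. The statement introducing the study, the virtual control group, the sample-size calculation and the secondary objective all point there. This also stands, and it makes the remedy easy: the hypothesis is the sentence that does not match the rest.

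Third, a reader might infer that a useless lens would be declared equal to the foreign designs in 26% to 41% of trials. That overstates the risk. Such a lens would also be compared with the 114 controls, and would pass both comparisons only about 2% of the time. The reply has limits: the Purpose joins the two comparators with and/or, so both are not required, and a half-effect lens passes both in about 26% of trials.

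Finally, the percentages depend on assumptions, notably the foreign SD and carrying a 60% effect over to the local rate. They should be quoted only with those conditions.

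**Conclusion.** The concern holds as a mismatch between hypothesis and analysis. Parity is the stated hypothesis and a foreign comparison is planned, but the plan supplies only difference tests and a sample size for a difference from controls. Beating natural history would support the secondary objective without showing parity, since a lens can do so with half the foreign effect.

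The half-effect lens is therefore the main case. If non-significance were read as parity, such a lens would pass that reading about three times in four or more. The no-effect figure is real for the foreign comparison alone, but it is not the main risk. All these figures rest on the inputs and assumptions listed in the working.

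Because efficacy is secondary and the remedy is mostly wording, this belongs at the low end of changes that should be made.

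**What to change.** 1. Reword the Working Hypothesis to match the design and the sample-size calculation: one-year progression with the national lens is slower than in the natural-history group.
2. Add to the Plan for Analysing the Results that the foreign-lens comparison is descriptive and is reported as a difference with its 95% CI, and that a non-significant difference will not be read as equal effectiveness.
3. Allow a claim of equal effectiveness only if that interval excludes a loss larger than a margin fixed and justified before analysis. State that this sample is unlikely to achieve it.

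Cost: wording in two sections and one interval calculation, with no new patients, visits or data. The downside is that the sponsor gives up the parity claim unless the interval supports it.

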mm diameter ring with the treatment,⁴⁰ the national design that was presented has a uniform +3.50 diopter power zone that alters the visual field by 5% at 10 degrees from the circular shaped fovea,³⁸ as presented at the International Myopia Conference a month ago. As it is known that positive defocus in 30-40 minutes of exposure modifies the axial length (measured with Lenstar) by 10 microns due to changes in the choroidal thickness,⁴² The national design has been tested on 17 volunteer subjects showing a significant change of 11 microns in the axial length of their eyes, suggesting this pilot study (in the process of being published) that the lenses should be effective in halting the progression of myopia, as changes in the choroid are the first event in the retinal message that governs ocular growth.⁴³ This, coupled with the survey that gave a good reading tolerance in 70% of the 17 respondents within a month of wearing them, was presented at the Conference and is in the public domain. Respondents found it difficult to walk around with these lenses because they are like an executive bifocal, but tolerated them well for reading at home, with small lateral movements of the head when reading A4 texts or the computer. It is therefore our intention to do a free field test with such lenses on a larger sample.

POPULATION

Consecutive patients between 8 and 16 years of age who attend the institutions accredited for this study. These institutions will be accredited only if they can perform routine studies for myopia control (refraction exam and optical biometry).

USE OF GLASSES

Once the eyeglass prescription has been written by the ophthalmologist, the enrolled patients will be seen in opticians accredited for this study in close proximity to the

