agree to take the test for one year, with no ocular pathology other than myopia, with spherical equivalent (sphere + 50% of the cylinder) between -0.50 D and -5.00 D, with astigmatism less than -2.00 D in each eye, with anisometropia less than -1.00 D, with keratometry less than 47.00 D in the most curved meridian. Genetic syndromes will not be included or ruled out. A complete ophthalmologic evaluation will be performed including tonometry, fundus, subjective refraction and refraction under cycloplegia with two drops of 1% cyclopentolate instilled 5' apart and performed 40' after the last drop. Visual acuities of the subjective refraction will be greater than 8/10 in each eye. Axillary length measurements with optical biometry will be performed at the beginning of treatment at follow-up and at the end of the study. New cycloplegic refractions will be performed during follow-up and at one year of treatment. A survey of habits and history, including reading, outdoors, ON-OFF contrast use, hours of schooling, age of onset of spectacle use and family history of high myopia (also likely use of devices to monitor these habits in selected group) will be conducted. A pair of spectacles and their frames will be provided free of charge to all children studied for one year with the special addendum of peripheral defocus treatment or laser treatment for contrast reduction depending on the treated group. The children will be instructed to wear the glasses especially in front of smartphones, tablets, PC's or books at home after five o'clock in the afternoon and until going to bed, every day of the week including Saturdays and Sundays. During the rest of the day they will use their usual correction without properly updated defocus. As defocus in experimental animals has more effect in stopping experimental myopia in the afternoon than in the morning,⁴⁴ It is expected that use in the afternoon only will be sufficient to achieve the effect. On the other hand, the peripheral contrast-lowering lens that has shown good tolerance and absence of visual field alteration will be used all day long by the subjects under treatment.

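### The optician's delivery instruction contradicts the evening-only schedule that METHODS sets for the defocus lens

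*Combined protocol and SAP*

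**What the plan says.** USE OF GLASSES describes the fitting visit. The optician checks adaptation and mobility in the shop, "instructing the child to wear the glasses at home for a couple of days and then to wear them for as long as possible". No lens type, time window or later limit on place is named.

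METHODS says the glasses are supplied "with the special addendum of peripheral defocus treatment or laser treatment for contrast reduction depending on the treated group", and then gives two schedules.

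- **Defocus lens:** worn at home, especially for screens and books, from five o'clock "in the afternoon and until going to bed, every day of the week including Saturdays and Sundays". The next sentence covers the remaining hours: "During the rest of the day they will use their usual correction without properly updated defocus". After citing animal work on time of day, the section concludes: "It is expected that use in the afternoon only will be sufficient to achieve the effect".
- **Contrast-lowering lens:** set against the first as a lens that "has shown good tolerance and absence of visual field alteration will be used all day long by the subjects under treatment".

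DEFOCUS GLASSES OF NATIONAL DESIGN says the treatment zone of the defocus lens "alters the visual field by 5% at 10 degrees from the circular shaped fovea". It also reports on the pilot: "Respondents found it difficult to walk around with these lenses", although reading at home was well tolerated.

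**The concern.** Both texts are instructions to the child about the same pair of glasses. After a short home phase, one sets no limit on wear. The other confines wear to the evening at home and assigns a different pair to the rest of the day. A child with the defocus lens cannot follow both.

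The instructions part exactly where this lens is known to be difficult. Tolerance is a primary objective, and EVALUATION OF TOLERANCE AND ADHERENCE scores it overall and also on reading and walking. A report of trouble when walking means one thing from a child who wears the lens at home in the evening, and another from a child who wears it at school and in the street. Progression, the secondary objective, would likewise be measured under an undefined daily exposure.

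**Working it through.** The plan gives no figure for wear time, so the check is a comparison of texts.

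**1. The instructions side by side**

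| | USE OF GLASSES | METHODS, defocus lens | METHODS, contrast-lowering lens |
|---|---|---|---|
| Lens named | none | yes | yes |
| Place | home at first, then no limit | home | none stated |
| Hours | as many as the child can manage | 17:00 to bedtime, 7 days a week | all day |
| Other hours | not addressed | usual correction | not applicable |
| Reason given | none | animal data on time of day | good tolerance, no field alteration |

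After its home phase, the delivery instruction is compatible with the third schedule but not with the second.

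**2. Could the delivery instruction concern only the contrast-lowering lens?** It names no lens. The lens-design section that precedes it describes only the defocus lens, and SAMPLE AND SAMPLE SIZE, which follows, names only a defocus group. The defocus lens cannot be read out of it.

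**3. Could it mean as long as possible within the evening window?** The section mentions no window. The order of the sentence, home first and then longer, moves away from home-only wear.

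**4. Could the evening be a priority rather than a limit?** The word meaning especially, in METHODS, applies to screens and books. The following sentence gives the rest of the day to the usual correction, and the rationale treats afternoon-only use as enough.

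**5. Which results are exposed?**

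- *Tolerance:* exposed, mainly through walking. The GOOD/BAD class that the plan applies to tolerance and adherence is cut on the child's tolerance answer, so it is exposed in the same way.
- *Adherence count:* not exposed. It is defined by failure to complete the three scheduled visits, whatever the hours worn.
- *Progression:* possibly exposed, because daily exposure is not fixed. Neither direction nor size can be derived.

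**6. What do the forms capture?** The month-1 survey (PART II. BIS) and the month-6 questionnaire (PART III (BIS)) ask about home wear, all-day wear, days not worn, and trouble when reading or walking. A YES to either wear item leads to the same tolerance questions, and neither answer is marked as the assigned regimen. PART IV, as shown, has no wear items.

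**The case against.** The best defence is that the two texts have different roles. USE OF GLASSES describes routine fitting advice. METHODS sets the study regimen in detail, with a rationale, and many readers would let the specific text govern. The advice also limits itself: a child who cannot walk in the lens is not told to do so. In addition, the wording of the training video on wear time is not given, and the informed consent annex is not in the available text. Either might state the schedule.

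Part of this stands. METHODS is probably the intended regimen, and the forms do record both patterns of wear. But the protocol states no order of precedence, and the optician's instruction is the one given when the child receives the glasses. A correct video or consent form would still leave the protocol contradicting itself.

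Three stronger readings are tempting, and the documents do not support them.

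- A reader might infer that children are split between two regimens. On the text, every child goes through the optician and every child is instructed under METHODS. The problem is an ambiguous instruction to all of them.
- A reader might infer that the whole primary objective is compromised. The visit-based adherence count does not depend on hours worn.
- A reader might want to size the gap in hours. Assuming bedtime at 21:00 to 23:00, the evening window is 4 to 6 hours. Assuming waking at 06:30 to 08:00, the ratio of waking day to window runs from 15/6 = 2.5 to 14.5/4 = 3.6. Those clock times are assumptions, and the ratio is an upper limit on prescribed wear. It says nothing about outcomes.

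**Conclusion.** The plan is wrong as written: it contains an internal inconsistency in the prescribed use of its main device. Every child with the defocus lens gets conflicting wear instructions, so the tolerance result, mainly for walking, and possibly the progression estimate would not refer to one defined regimen. The size of any effect cannot be derived from the documents.

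The conclusion assumes that the video and the consent annex do not already override the delivery instruction. If they do, the practical risk falls but the contradiction in the protocol remains. It should be corrected before glasses are handed out, because wear reports can describe mixed use afterwards but cannot undo it.

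**What to change.** 1. In USE OF GLASSES, replace the wear clause with an instruction to follow the schedule that METHODS gives for the child's lens type. A cross-reference is safer than a restatement: it keeps the emphasis on screens and books for the defocus lens, and adds no home phase for the contrast-lowering lens that METHODS does not contain.
2. If all-day defocus wear is what the investigators want, amend METHODS instead, including the usual-correction sentence and the afternoon-only rationale.
3. Make the training video for opticians and ophthalmologists say the same.
4. In the defocus group, describe overall, reading and walking tolerance by the existing home-wear and all-day-wear answers at months 1 and 6. With 50 children planned, this is descriptive only.

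The cost is one edited clause, a check of the video and a small additional table. No new visits, participants or data items are needed.
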